#### **4.2. Exclusion Criteria**

These exclusion criteria apply to subjects who have participated in Studies A0081041, A0081042, or A0081105, as well as those subjects who have not. In order for Direct Enrolling Subjects to be eligible, all exclusion criteria should be confirmed prior to, or on, Visit 2.

Subjects presenting with any of the following will not be included in the study:

1. Lennox-Gastaut syndrome, Infantile Spasms, Absence seizures for Direct Enrolling subjects, BECT (Benign epilepsy with centrotemporal spikes) and Dravet syndrome. A current diagnosis of febrile seizures, any febrile seizures within 1 year of screening, or seizures related to an ongoing acute medical illness.

Prior history (ie, more than 1 year prior to screening) of febrile seizures may be allowed on a case by case basis following consultation with study clinician.
2. Status epilepticus within 1 year prior to Visit 1 of this study.
3. Seizures related to drugs, alcohol, or acute medical illness.
4. Progressive structural central nervous system (CNS) lesion or a progressive encephalopathy. Progressive inborn errors of metabolism.
5. Known or suspected chronic hematologic, hepatic or renal disease (aspartate aminotransferase –AST- and alanine aminotransferase –ALT- above 3 times the upper limit of normal; or bilirubin, BUN, or creatinine above 2 times the upper limit of normal within the previous 6 months for infants, children and adolescents aged 6 months or more, or at any postnatal period for infants younger than 6 months). Estimated creatinine clearance (CLcr) <60 mL/min for subjects  $\geq 17$  yr and <80 mL/min/1.73m^2 (using age appropriate equations) for subjects <17 years of age. For subjects who previously participated in A0081041, A0081042 or A0081105, it is assumed the subjects have already met entry criteria, therefore, the creatinine clearance exclusion is based upon results collected at the Screening Visit laboratory of A0081041, A0081042 or A0081105. The laboratory exclusion criteria noted above will be based upon data collected at the Last visit (Visit 9, Early Termination, or Unscheduled Visit) of the A0081041, A0081042 or A0081105.
6. Other severe acute or chronic medical (eg, genetic or chromosomal syndromes) or psychiatric condition or laboratory abnormality that may increase the risk associated with study participation or investigational product administration or may interfere with the interpretation of results and, in the judgment of the investigator or the sponsor, would make the subject inappropriate for entry into this study.
7. Pregnant or nursing females (females who are menarchal must have a negative urine pregnancy test); menarchal females of childbearing potential who are unwilling or

unable to use an acceptable method of contraception, as outlined in the protocol, until completion of follow-up procedures.

8. Taking any non-antiepileptic (non-AED) medication that could alter the effectiveness of the subject's medication, response, seizure frequency or characteristics. Medications for Attention Deficit/Hyperactivity Disorder and other behavioral changes (eg, risperidone) will be permitted. A ketogenic diet will also be allowed given that the diet is adhered to for the duration of the study. Note: changes in the dose, regimen and type of these medications during study participation may be allowed upon discussion with the study clinician. Continued participation of the subject will be evaluated and decided on a case-by-case basis.
9. Taking or have taken any other investigational drug (aside from participation in Studies A0081041, A0081042 or A0081105) within the last 30 days prior to screening.
10. The concomitant use of gabapentin, felbamate and vigabatrin is prohibited.
11. Use of cocaine, phencyclidine (PCP), or other illegal or illicit drugs is prohibited. Use of marijuana, or its derivatives, including prescribed medical marijuana, is not allowed under any circumstances. Use of amphetamines, barbiturates, opiates, or benzodiazepines without a valid current prescription is prohibited.
12. Unwilling or unable to comply with the [Life Style Guidelines](#).
13. Subjects not reasonably expected to complete the study.
14. Any subjects considered at risk of suicidal behavior based upon the Columbia Suicidality Rating Scale (C-SSRS) Lifetime (subjects  $\geq 6$  years of age) or Child Behavioral Check List (CBCL)(subjects  $< 6$  years of age) or responses obtained during the Modified International Neuropsychiatric Interview (MINI-KID). A subject should be excluded or a risk assessment should be done by a qualified mental health professional based on responses to assessment of suicidal ideation and behavior and if the subject has had suicidal ideation in the last 6 months prior to screening, suicidal behaviors or attempts in the past year, or current major psychiatric disorders that are not explicitly permitted in the inclusion/exclusion criteria. A risk assessment should also be performed in any child  $< 6$  years of age who has ever exhibited any potentially self-injurious or high-risk behaviors such as hurting himself or herself, or unusual behaviors such as running into traffic or using items as weapons (eg, knife, bat). Any concerns regarding such behaviors should be discussed with the Pfizer clinician prior to study participation or continuation.
15. For subjects who have not participated in Studies A0081041, A0081042, or A0081105 and enrolling directly into Study A0081106, treatment with pregabalin for any reason within 60 days prior to screening, or prior participation in a pregabalin clinical study is prohibited.

16. Known allergy or intolerance to pregabalin or its excipients, including lactose, or other  $\alpha 2\delta$  ligands (eg, gabapentin).
17. Subjects, or subjects whose parents/legally acceptable representatives are investigational site staff members; and subjects, or subjects whose parents/legally acceptable representative are Pfizer employees directly involved in the conduct of the study.

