treatment of Generalized Anxiety Disorder (GAD) in adults. The efficacy of pregabalin in subjects with PGTC seizures has not been assessed to date in a placebo-controlled study. The approved dose range for the adjunctive treatment of partial onset seizures in adults is 150 to 600 mg/day, administered 2 times (BID) or 3 times (TID) a day. The most common adverse effects reported with pregabalin in placebo-controlled adjunctive trials of pregabalin in adults with partial onset seizures were dizziness and somnolence. Since initial market approval of Lyrica® in 2004, it is estimated that more than 11,700,000 patient-years of exposure will have accumulated worldwide. More detailed information, including efficacy results in adults and the possible risks associated with administration of pregabalin, are summarized in the Investigator's Brochure which will serve as the Single Reference Safety Document for this study.

Pregabalin pharmacokinetic (PK) data from adult clinical pharmacology studies and one clinical pharmacology study in pediatric subjects with epilepsy (Study A0081074) show that pregabalin pharmacokinetics are linear and predictable. Multiple-dose pharmacokinetics are predictable from single-dose data. Pregabalin is rapidly absorbed when administered in the fasted state, with oral bioavailability of  $\geq 90\%$  and peak plasma pregabalin concentrations occurring 0.7 to 1.5 hours following both single- and multiple- dose administration.

Pregabalin can be dosed either 2 or 3 times a day. Pregabalin is essentially not metabolized and administration with food has no clinically relevant effect on the total amount of pregabalin absorbed. Pregabalin is eliminated from the systemic circulation primarily by renal excretion as unchanged drug, with a mean plasma pregabalin half-life of 6.3 hr in adults. Pregabalin terminal  $t_{1/2}$  averaged about 3 to 4 hours in pediatric subjects from 1 month to 6 years of age, and 4 to 6 hours in those 7 years of age and older. Pregabalin oral clearance normalized per body weight was 43% higher in the children with body weight less than 30 kg than in children whose body weight was 30 kg and higher. Pregabalin clearance is proportional to creatinine clearance, and the major influence on its clearance is reduced or impaired renal function.

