#### Estimated Creatinine Clearance (ml/min)

Estimated Creatinine Clearance will be calculated at Screening (Visit 1A or 1B) only. For subjects who previously participated in A0081041, A0081042 or A0081105, it is assumed the subjects have already met entry criteria, therefore, the Creatinine Clearance exclusion is based upon the Screening visit of A0081041, A0081042 or A0081105. For those subjects directly enrolling into A0081106, this assessment is to be performed at Screening Visit 1B only. The estimation will be calculated by the central laboratory using the following equation, the subject's age in years and the serum creatinine value (mg/dL).

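### For roll-over subjects the creatinine clearance limit is judged on an older sample than serum creatinine itself, so a subject whose current clearance is below the limit can enter without it being calculated

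*Protocol*

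**What the plan says.** Protocol Section 4.2 applies its exclusion criteria to roll-over and direct-enrolling subjects alike. Criterion 5 excludes an estimated CLcr below 60 mL/min from age 17, or below 80 mL/min/1.73 m² under 17. It also excludes AST or ALT above 3 × ULN, and bilirubin, BUN or creatinine above 2 × ULN.

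For subjects from A0081041, A0081042 or A0081105 the criterion then uses two sampling dates:

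- CLcr: "the creatinine clearance exclusion is based upon results collected at the Screening Visit laboratory of A0081041, A0081042 or A0081105". The reason given is that "it is assumed the subjects have already met entry criteria".
- The rest: "The laboratory exclusion criteria noted above will be based upon data collected at the Last visit" of the parent study.

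Section 7.3 opens with "Estimated Creatinine Clearance will be calculated at Screening (Visit 1A or 1B) only". It then repeats the parent-screening rule for roll-over subjects and assigns the Visit 1B calculation to direct enrollers. Section 6.1 reuses parent-study chemistry, height and weight at Visit 1A.

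On why renal function matters, Section 1.2 states: "Pregabalin clearance is proportional to creatinine clearance, and the major influence on its clearance is reduced or impaired renal function".

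**The concern.** A newer creatinine is already reviewed for eligibility but is not put through the CLcr equations. The limit that the protocol ties most directly to drug clearance is thus the one judged on the oldest sample. A subject whose renal function fell during the parent study can start 12 more months of treatment with a current CLcr below the stated limit, and nothing requires anyone to work it out. The next scheduled chemistry is Visit 6, Month 6 (Section 7.3.3), and no later CLcr is planned.

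The text is also unclear. CLcr is itself a laboratory criterion noted above the last-visit sentence in Section 4.2, so that sentence can be read as covering it. The opening sentence of Section 7.3 does not fit the two that follow.

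**Working it through.** The plan gives no figure of its own to reproduce. The check asks whether the last-visit creatinine rule already does the work of the CLcr limit.

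**Inputs from the protocol.** Limits of 80 (under 17 years) and 60 (17 and over), and exclusion for creatinine above 2 × ULN, so that exactly 2 × ULN passes (Section 4.2). Equations from Section 7.3, with SCr as serum creatinine in mg/dL:

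- 1 to under 12 months: 0.45 × length / SCr
- 1 to under 12 years: 0.55 × length / SCr
- 12 years and over: (140 − age) × weight / (72 × SCr) × 1.73/BSA, times 0.85 for females

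**Assumptions.** The documents give no ULN and no body sizes. Both are assumed, with the ULN shown as a range.

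**Step 1: CLcr at the highest creatinine that still passes.** For a 115 cm child, 0.55 × 115 = 63.25. Dividing by 1.0 gives 63.3, and by 1.4 gives 45.2.

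| Assumed subject | Assumed ULN | Creatinine at 2 × ULN | CLcr | Limit |
|---|---|---|---|---|
| Infant, 60 cm | 0.3–0.5 | 0.6–1.0 | 45–27 | 80 |
| Child, 115 cm | 0.5–0.7 | 1.0–1.4 | 63–45 | 80 |
| Child, 140 cm | 0.6–0.8 | 1.2–1.6 | 64–48 | 80 |
| Boy, 14 y, 50 kg, 160 cm | 0.9–1.0 | 1.8–2.0 | 56–50 | 80 |
| Man, 30 y, 70 kg, 175 cm | 1.0–1.2 | 2.0–2.4 | 50–42 | 60 |

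The adult limit is in mL/min, while the equation is scaled to 1.73 m². Without the BSA factor the man's values are 53.5 to 44.6, so the result is the same either way. The gap closes only at a low ULN: for the 115 cm child at about 0.40 mg/dL or less (0.55 × 115 / 80 / 2), and for the man at about 0.83 or less (scaled).

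**Step 2: how small a change is enough.** At unchanged length, a child with CLcr 90 at parent screening reaches 80 when creatinine rises by 90/80 − 1 = 12.5%. At unchanged age and weight, an adult at 70 reaches 60 with a rise of 70/60 − 1 = 16.7%.

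**Step 3: how old the screening value is.** SAP Appendix 1 gives A0081105 an 8-week baseline counted from screening. Protocol Section 4.1 requires at least 4 weeks of double-blind treatment. For these subjects the value is at least about 8 + 4 = 12 weeks old, and older for those who completed treatment and taper. The documents do not allow the same sum for A0081041 or A0081042.

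**Step 4: what it could mean for exposure.** If clearance is proportional to CLcr, exposure at a given dose, relative to a child at the limit of 80, is 80/63.3 = 1.26 to 80/45.2 = 1.77 times. Assume the 115 cm child weighs under 30 kg, where the dose levels run from 3.5 to 14 mg/kg/day. At the ratio of 1.77, the lower two levels correspond to 6.2 and 12.4, both still within that range, and the upper two (10.5 and 14) to 18.6 and 24.8. At 1.26, only the top level exceeds the range (17.6).

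**The case against.** The strongest reply is that the rule is deliberate. Section 4.2 states it with a reason, Section 7.3 repeats it, and the Amendment 1 entry in the Document History shows that the calculation was meant for direct enrollers only. That stands. A reader might infer that a roll-over subject with a low current CLcr has failed an exclusion or violates the protocol. The documents do not support this, because for these subjects they define the exclusion on the parent screening value.

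There are other safeguards. Criterion 5 also names known or suspected chronic renal disease. Criterion 6 lets the investigator or sponsor exclude for a laboratory abnormality that raises risk, and unscheduled visits and blood tests are possible. These reduce the concern, but they are discretionary and none requires CLcr to be recalculated.

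The figures in Step 1 are boundary cases. A 115 cm child exactly at 80 had a creatinine of 0.79 mg/dL, and reaching 1.4 needs a 77% rise. This too stands, although Step 2 shows that far smaller rises can cross the limit.

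A reader might also infer that exposure in such subjects exceeds the intended range, or that their adverse events would be misattributed. Neither follows. Dosing starts at the lowest level and is flexible on tolerability, and Step 4 shows lower dose levels staying inside the range. Causality is judged event by event (Section 8.9), and no PK/PD endpoint is planned.

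Finally, Visit 1A falls on the parent study's last day and chemistry goes to a central laboratory, so a result may not be back before dispensing. That difficulty already applies to the last-visit creatinine, AST, ALT, bilirubin and BUN rules. CLcr from the same sample adds almost nothing to it.

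**Conclusion.** The point holds as a mismatch of sampling dates within one criterion, together with wording in Section 7.3 that does not agree with itself. The 2 × ULN creatinine rule does not replace the CLcr limits under the protocol's own equations: across the assumed cases, values of 27 to 64 pass against a limit of 80, and 42 to 50 (BSA-scaled) against 60. A roll-over subject whose current CLcr is below the stated limit can therefore enter without it being calculated.

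The size rests on assumed ULNs and body sizes and describes the worst value that passes, not a typical one. The number of subjects affected cannot be estimated, because the documents give no creatinine distribution. At a given mg/kg dose, exposure can be higher than intended, up to about 1.8 times that at the limit in the 115 cm example, but it need not be. This conclusion takes no view on whether 60 and 80 are the right limits.

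**What to change.** Reconcile criterion 5 of Section 4.2 with Section 7.3 so that one sample governs all renal and laboratory exclusions for roll-over subjects. The way that uses existing data is for the central laboratory to report CLcr from the last-visit creatinine already used for the other exclusions, with the height and weight on record, against the existing limits. Section 7.3 should then say plainly what Visit 1A means for the calculation, and Section 6.1 should say which parent-study visit supplies the height and weight.

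The cost is one calculation per roll-over subject, with no new blood draw or visit. The downside is that a few roll-over subjects may be found ineligible, possibly after results return, as can already happen with the other last-visit exclusions. The repeat-test and withdrawal note for exclusionary results appears only under Visit 1B (Section 6.2), so the sponsor should also state how a late result is handled for roll-over subjects.

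If the sponsor keeps the parent-screening value, the two sections should still be made to agree, with the reason for using different samples stated.

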#### **4.3. Life Style Guidelines**

Subjects should be advised that pregabalin may cause dizziness and somnolence. Accordingly, as age appropriate, subjects should be advised not to drive, consume alcohol or operate complex machinery until they have gained sufficient experience on study drug to assess its effects on performance.

##### **4.3.1. Contraceptive Guidelines**

The investigator should interview each subject to obtain his/her sexual and contraceptive history in order to give appropriate sexual counseling about conduct during the study. All subjects (male and female) with reproductive potential must agree to practice simultaneously 2 effective contraception methods or abstinence for at least 28 days prior to the first dose of study drug and for 28 days following the last dose of study drug. These may include:

- Barrier (condoms, diaphragm or cervical cap) with spermicide.
- Oral or other acceptable contraceptives which may include but is not limited to: injectable, implanted or patch hormone therapy, IUD, or documented surgical sterilization.
- Absolute sexual abstinence, without a second method.

A urine pregnancy test for female subjects who are menarchal will be collected at Visits 1, 6, 7, and 8. If the results of the urine pregnancy test are positive, the subject will not be eligible for study participation.

#### **4.4. Sponsor Qualified Medical Personnel**

The contact information for the sponsor's appropriately qualified medical personnel for the trial is documented in the study contact list located in the team Sharepoint.

To facilitate access to appropriately qualified medical personnel on study related medical questions or problems, subjects are provided with a contact card. The contact card contains, at a minimum, protocol and investigational compound identifiers, patient study number, contact information for the investigational site and contact details for a help desk in the event that the investigational site staff cannot be reached to provide advice on a medical question or problem originating from another healthcare professional not involved in the subjects participation in the study. The help desk number can also be used by investigational staff if they are seeking advice on medical questions or problems, however it should only be used in

the event that the established communication pathways between the investigational site and the study team are not available. It is therefore intended to augment, but not replace the established communication pathways between the investigational site and study team for advice on medical questions or problems that may arise during the study. The help desk number is not intended for use by the subject directly and if a subject calls that number they will be directed back to the investigational site.

#### **4.5. Rater Qualifications**

The process of reviewing rater qualifications, approval of raters for training and the training of raters is administered by **CCI** as an agent of the Sponsor. All designated raters must complete a Rater Qualification Survey available through the study web-based workspace **CCI** in order to become qualified as a rater. All site personnel who require or request access to the workspace are granted access upon site activation. All qualified raters must also successfully complete protocol required training prior to the administration of any assessment (ie, Mini-Kid; CBCL; C-SSRS – please see [Section 7-ASSESSMENTS-](#) for additional details). The assessment instruments have been designed for use by professionals who have been trained on their administration. Therefore, all raters must complete the required assessment training, either during attendance at an Investigator Meeting, or through the study web-based workspace. All training materials and instructions are located on the workspace. The company **CCI** will issue a rater training completion certificate to qualified raters for training on each assessment instrument that has been completed. Qualified raters must have a valid rater training completion certificate on file in order to perform the assessment.

### **5. STUDY TREATMENTS**

#### **5.1. Allocation to Treatment**

Subjects who complete Visit 1 and meet the eligibility criteria will begin study treatment.

Subjects will be assigned sequentially a subject number at the time of screening (Visits 1A or 1B) by a telerandomization system. An IVRS drug supply management system will assign study medication by assigning appropriate container numbers.

Pediatric subjects with body weight  $\geq 30$  kg will initiate dosing of pregabalin at the daily dose of 2.5 mg/kg/day administered in 2 equally divided doses (BID) in subjects  $\geq 4$  years of age or in 3 equally divided doses (TID) in subjects  $< 4$  years of age for a minimum of 1 week. Thereafter, dosing will be flexible, based on individual seizure response and tolerability. Doses may be adjusted up or down at clinic visits in increments of no more than 2.5 mg/kg/day to daily dose levels of 5.0, 7.5, or 10.0 mg/kg/day. For pediatric subjects with body weight  $< 30$  kg, the daily dose will be adjusted by 40% to an initial daily dose of 3.5 mg/kg/day administered in 2 equally divided doses (BID) in subjects  $\geq 4$  years of age or in 3 equally divided doses (TID) in subjects  $< 4$  years of age for a minimum of 1 week. Thereafter, dosing will be flexible, based on individual seizure response and tolerability. Doses may be adjusted in increments of no more than 3.5 mg/kg/day to daily dose levels of 7.0, 10.5, or 14.0 mg/kg/day. Subjects will maintain a BID or TID dosing regimen throughout study participation based on age at Visit 1 (especially for subjects rolling over

from Study A0081042 who will remain on a TID regimen) to avoid potential dosing error/noncompliance related to regimen switch.

Adult subjects who enroll in this study following participation in Study A0081105 will initiate dosing of pregabalin at the level of 150 mg/day administered daily in 2 equally divided doses (BID) of 75 mg. Thereafter, dosing will be flexible and based on individual seizure response and tolerability. Doses may be adjusted in increments of no more than 150 mg/day to daily dose levels of 300, 450, or 600 mg/day.

The investigator's knowledge of the treatment should not influence the decision to enroll a particular subject or affect the order in which subjects are enrolled.

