### **Study Treatments:**

A0081106 study medication will be provided as pregabalin liquid oral solution or oral capsules. Subjects <4 years of age at Visit 1 or who are enrolling from A0081042 will receive study medication 3 times daily (TID) in equally divided doses. Subjects who are  $\geq 4$  years of age at Visit 1 will receive study medication twice daily (BID) in equally divided doses.

- All eligible pediatric subjects 1 month to 16 years and 11 months of age will take pregabalin in Study A0081106 at a dosage according to their body weight:
  - Pediatric subjects weighing  $\geq 30$  kg will begin pregabalin dosing at 2.5 mg/kg/day (maximum 150 mg/day). Subjects will remain at the starting dose for 8 days until Visit 2. Thereafter, dosing will be flexible based on individual seizure response and tolerability. Pediatric subjects may have their dose adjusted up or down at clinic visits in increments of no more than 2.5 mg/kg/day (maximum 150 mg/day) to daily dose levels of 5.0 (maximum 300 mg/day), 7.5 (maximum 450 mg/day), or 10.0 mg/kg/day (maximum 600 mg/day).
  - Pediatric subjects with body weight <30 kg will begin pregabalin dosing at 3.5 mg/kg/day until Visit 2. Thereafter, dosing will be flexible based on individual seizure response and tolerability. Pediatric subjects may have their dose adjusted up or down at clinic visits in increments of no more than 3.5 mg/kg/day to daily dose levels of 7.0, 10.5, or 14.0 mg/kg/day. This 40% higher dose per kg in pediatric subjects with body weight <30 kg is needed to achieve exposures similar to those of adults or pediatric subjects weighing  $\geq 30$  kg.
- All eligible adult subjects 17 to 65 years of age will begin dosing of pregabalin in Study A0081106 at the level of 150 mg/day. Subjects will remain at this dose for 8 days until Visit 2. Thereafter, dosing will be flexible based on individual seizure response and tolerability. Adult subjects may have their dose adjusted up or down at

clinic visits in increments of no more than 150 mg/day to dose levels of 300, 450, or 600 mg/day.

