### **1.3 Dose Rationale**

The recommended dosing regimen in both the US and EU for adjunctive therapy with Lyrica® in adults with partial onset seizures ranges from 150 to 600 mg/day given BID or TID. The recommended dose range in adults is approximated by the 2.5 mg/kg/day to 10 mg/kg/day pregabalin dose range for pediatric subjects <60 kg in this study. This range of doses is anticipated to provide efficacy for the subjects enrolled and will characterize safety and tolerability of this dose range for pediatric subjects.

Doses in the range of 2.5 to 15 mg/kg/day were studied in pediatric subjects between 1 month and 16 years of age in Study A0081074 and serial blood samples were collected to assess the pharmacokinetics of pregabalin in the pediatric population. Data from Study A0081074 were compared with the adult data in a population pharmacokinetic analysis which showed that the relationship between creatinine clearance (CLcr) and pregabalin clearance (CL/F) was similar between both populations. Therefore, knowing a subject's CLcr value, the pregabalin oral clearance and thus pregabalin exposure can be estimated with a high degree of accuracy.

The noncompartmental and population pharmacokinetic analyses utilizing data from pediatric subjects from Study A0081074 indicated that for subjects with body weight  $\geq 30$  kg exposure equivalent to that observed in adults would be achieved when the pediatric subjects were dosed on a mg/kg/day basis. Due to higher clearance/kg in pediatric subjects with body weight  $< 30$  kg, a daily dose/kg 40% higher is needed to achieve exposure similar to that of adults or pediatric subjects weighing  $\geq 30$  kg. Thus, pediatric subjects with body weight  $\geq 30$  kg will initiate dosing at the daily dose of 2.5 mg/kg/day for a minimum of 1 week. Thereafter, dosing will be flexible, based on individual seizure response and tolerability. Doses may be adjusted up or down at clinic visits in increments no more than of 2.5 mg/kg/day. For pediatric subjects with body weight  $< 30$  kg, the daily dose will be adjusted by 40% to an initial daily dose of 3.5 mg/kg/day for a minimum of 1 week. Thereafter, dosing will be flexible, based on individual seizure response and tolerability. Doses may be adjusted up or down at clinic visits in increments of no more than 3.5 mg/kg/day.

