#### **3.1. Treatments and Visits**

[figure not shown]
The day of the last visit (completion of taper phase) of Studies A0081041, A0081042, and A0081105 is designated as Day 1 (Visit 1A) of this study. Baseline values for analysis of change in safety endpoints will be the assessments made prior to initiating double-blind dosing at Visit 1 of Studies A0081041, A0081042, or A0081105. For subjects directly entering Study A0081106 without participation in one of the studies above, baseline values for analysis of change in safety endpoints will be the assessments made at the first visit (Screening Visit 1B) of this study.

For pediatric subjects, pregabalin dosing will initiate at the daily dose of 2.5 mg/kg/day (subjects  $\geq$ 30 kg) or 3.5 mg/kg/day (subjects  $<$ 30 kg) at this visit. Adult subjects who enroll in this study following participation in Study A0081105 will initiate dosing at 150 mg/day. All seizures experienced will be self-recorded by the subject or recorded by their parents/legally acceptable representative as appropriate, in a daily seizure diary beginning at Visit 1 and subsequently throughout the entire study.

Subjects will return for the designated assessments of safety, tolerability, and drug accountability at Week 1 (Visit 2), Month 1 (Visit 3), Month 2 (Visit 4), Month 4 (Visit 5), Month 6 (Visit 6), Month 9 (Visit 7), Month 12/Early Termination (Visit 8), and Follow-up (Visit 9). Investigator site staff will contact the subject and/or parent/caregiver by telephone at least monthly between visits, to address questions, assess safety and adverse events, and ensure compliance with study directives.

At Visit 2 and subsequent visits thereafter, the investigator or designee will review seizure diary data and tolerability with the subject and may adjust the dose at his/her discretion. For pediatric subjects with body weight  $\geq 30$  kg (1 month to 16 years of age), doses may remain the same or be adjusted upward in increments of no more than 2.5 mg/kg/day to daily dose levels of 5.0, 7.5, or 10.0 mg/kg/day. For pediatric subjects with body weight  $< 30$  kg, doses may be adjusted in increments of no more than 3.5 mg/kg/day to daily dose levels of 7.0, 10.5, or 14.0 mg/kg/day. For adult subjects (17 to 65 years of age) doses may be adjusted in increments of 150 mg/day to daily dose levels of 300, 450, or 600 mg/day.

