### **5.2.3. Administration**

Pregabalin will be administered orally daily in 2 equally divided doses (BID; approximately q12 hr) in subjects  $\geq$ 4 years of age or in 3 equally divided doses (TID; approximately q8 hr) in subjects  $<$ 4 years of age, as specified in [Section 5.1- Allocation to Treatment](#). Subjects weighing  $<$ 30 kg will receive pregabalin as a liquid formulation. Pediatric and adult subjects

with body weight  $\geq 30$  kg may choose either liquid or capsule formulation based on subject preference and ability to swallow the size # 0 capsules. Study medication formulation for administration will be as outlined below, with investigators (and subjects) determining the choice of solution or capsule for children and adults  $>30$  kg.

If a subject missed a dose, subject should skip the dose and wait until the next scheduled dose for administration. No additional study medication administration (ie, double-dosing) is allowed at any time during the study.

Weight	Formulation
<30 kg	Liquid
Pediatric subjects $\geq 30$ kg	Liquid or capsule
Adult subjects	Capsules or liquid

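### Protocol Sections 3.1 and 5.1 leave out the mg/day maxima for pediatric subjects of 30 kg or more, so above 60 kg they give higher doses than the Protocol Summary allows

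*Protocol*

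**What the plan says.** **Protocol Summary, Study Treatments.** Pediatric subjects of at least 30 kg "will begin pregabalin dosing at 2.5 mg/kg/day (maximum 150 mg/day"), and may then move "to daily dose levels of 5.0 (maximum 300 mg/day), 7.5 (maximum 450 mg/day), or 10.0 mg/kg/day (maximum 600 mg/day"). The increment of 2.5 mg/kg/day is also limited to 150 mg/day.

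**Section 3.1.** For the same subjects "pregabalin dosing will initiate at the daily dose of 2.5 mg/kg/day", and doses may then stay the same or be "adjusted upward in increments of no more than 2.5 mg/kg/day to daily dose levels of 5.0, 7.5, or 10.0 mg/kg/day". No mg/day limit is given.

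**Section 5.1.** The start is 2.5 mg/kg/day, and doses may be moved up or down "at clinic visits in increments of no more than 2.5 mg/kg/day to daily dose levels of 5.0, 7.5, or 10.0 mg/kg/day". Again there is no mg/day limit. The same section does limit adults in mg/day: "Doses may be adjusted in increments of no more than 150 mg/day to daily dose levels of 300, 450, or 600 mg/day".

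**Section 1.3.** The start and increment appear without a maximum. The section says the adult range is approximated by the 2.5 to 10 mg/kg/day "pregabalin dose range for pediatric subjects <60 kg in this study".

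**Taper (Section 3.1 text and Table 1).** The recommended schedule for pediatric subjects of 30 kg or more is given in mg/kg/day only. The adult schedule (Table 3) is in mg/day.

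**The concern.** The protocol contains two dosing rules for the same subjects, and they diverge above 60 kg. The rule without caps is the one in the treatment section. Nothing in the readable text of Sections 3.1 or 5.1 refers back to the Summary, and no eligibility criterion sets an upper weight limit, so a heavy adolescent can enrol.

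A site following Section 5.1 literally could give an 80 kg 16-year-old 800 mg/day, while an 80 kg adult in the same study stops at 600 mg/day. Section 1.2 gives the approved adult range as 150 to 600 mg/day. Section 1.3 says 2.5 to 15 mg/kg/day was studied in children, but without weights or mg/day doses, so it does not show that more than 600 mg/day was covered.

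Record-keeping is affected too. Section 8.4 makes dosing errors reportable, and SAP Section 5.6 calls for a listing of protocol deviations. For 700 mg/day in a 70 kg adolescent, the Summary implies a deviation and Section 5.1 does not.

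**Working it through.** **Inputs.** Levels and caps come from the Protocol Summary. The uncapped levels come from Sections 3.1 and 5.1. The weights of 65 to 90 kg are illustrative, because the documents give no weight distribution.

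**1. Weight at which each cap binds** = cap / level:

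- 150 / 2.5 = 60 kg
- 300 / 5.0 = 60 kg
- 450 / 7.5 = 60 kg
- 600 / 10.0 = 60 kg

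The result is the same at every level and matches the 60 kg qualifier in Section 1.3. At 60 kg or less the two rules agree.

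**2. Dose under each rule.** Sections 3.1 and 5.1: level × weight. Summary: the smaller of level × weight and the cap. Above 60 kg the ratio is weight/60 at every level.

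| Weight | 2.5 level (cap 150) | 5.0 level (cap 300) | 7.5 level (cap 450) | 10.0 level (cap 600) | Ratio to cap |
|---|---|---|---|---|---|
| 60 kg | 150 | 300 | 450 | 600 | 1.000 |
| 65 kg | 162.5 | 325 | 487.5 | 650 | 1.083 |
| 70 kg | 175 | 350 | 525 | 700 | 1.167 |
| 80 kg | 200 | 400 | 600 | 800 | 1.333 |
| 90 kg | 225 | 450 | 675 | 900 | 1.500 |

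Cells are the uncapped mg/day doses.

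**3. Subjects under 30 kg.** Their highest level is 14.0 mg/kg/day, and 14.0 × 30 = 420 mg/day, below 600. The gap therefore concerns only the group of 30 kg or more.

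**4. Taper (secondary).** Take a 90 kg subject at the 7.5 level, capped at 450 mg/day.

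- Read by assigned level, the 7.5 row gives 5.0 × 90 = 450 mg/day for 4 days, which is no reduction, then 2.5 × 90 = 225 mg/day for 3 days.
- Read by actual dose, 450 / 90 = 5.0 mg/kg/day, and the 5.0 row gives 225 mg/day for 7 days.
- Adult Table 3 for 450 mg/day gives 300 for 4 days, then 150 for 3 days.

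The 600 mg/day issue does not extend to the taper at ordinary weights: its highest dose, 5.0 mg/kg/day, passes 600 mg/day only above 600 / 5.0 = 120 kg.

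**The case against.** The strongest reply is that this is an omission and not a contradiction. The Summary belongs to the same protocol and states the maxima explicitly. Sections 3.1 and 5.1 never say that a pediatric dose may exceed 600 mg/day, and both texts can be followed at once by applying the listed level subject to the cap. Section 1.3 points the same way. Medication is also dispensed through the IVRS, which may already enforce the caps. The 75, 150, 225 and 300 mg capsules give exactly 150, 300, 450 and 600 mg/day when taken twice daily.

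Most of this stands as evidence of intent, and it is why overdosing cannot be presumed. It does not repair the text. A reader who uses Section 5.1 alone gets a different dose, including a different starting dose. The IVRS rule is not in the documents: Sections 6.1, 6.2 and 7.2 describe weight-based dosing without mentioning a maximum. The capsule strengths also serve the adult levels, and the 200 mg capsule would allow 400 mg twice daily.

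Three narrower objections are fair. The reference from Section 5.2.3 to Section 5.1 mainly concerns BID or TID frequency, so it adds little here. The taper is only recommended, which limits the weight of that point. Which visit weights set the dose (every visit in Sections 6.1 and 6.2, Visits 1 and 6 in Section 7.2) is a separate question.

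**Conclusion.** The concern holds and should be fixed. Sections 3.1 and 5.1 state the dosing rule for pediatric subjects of 30 kg or more without the maxima in the Protocol Summary. As written they give weight/60 times the Summary dose to anyone above 60 kg, and at 10 mg/kg/day they exceed the study's adult maximum.

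The textual difference and the arithmetic are certain. The practical consequence is conditional on a site following the body text and on the IVRS not applying the caps. The number of subjects aged 16 or under above 60 kg is unknown, and nothing shows that anyone was dosed above a cap. The study design figure is not reproduced and could not be checked. No planned summary changes, because SAP Section 8 combines all doses. The issue is patient protection and a clear standard for what counts as a dosing deviation.

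**What to change.** - In Sections 3.1 and 5.1, give each level its maximum: 2.5 (150 mg/day), 5.0 (300 mg/day), 7.5 (450 mg/day) and 10.0 mg/kg/day (600 mg/day).
- In Section 1.3, add the 150 mg/day maximum to the starting dose and the increment.
- Index the taper text and Table 1 by assigned dose level, with maxima of 300 mg/day at the 5.0 step and 150 mg/day at the 2.5 step. Above 60 kg this yields 600→300→150, 450→300→150, 300→150, and 150→0, which are the four rows of adult Table 3.
- Confirm that the IVRS applies these caps during treatment and taper. While that specification is open, state which visit weights it uses.

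The cost is wording in an amendment or administrative letter and one check of the IVRS specification. No new data, visits or analyses are needed.
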